7.5.1. Definitions

ECG abnormalities will be determined according to the boundaries defined in [Attachment 4](#).

An abnormality (based on normal ranges) will be considered treatment-emergent if it is worse than the baseline abnormality. If the baseline abnormality is missing, the abnormality is always considered as treatment-emergent. A shift from "abnormally low" at baseline to "abnormally high" post-baseline (or vice versa) is also treatment-emergent. The treatment-emergent definition is applicable in both, the treatment and follow-up phase.

Assessments taken while the subject was not in a supine position will not be included in descriptive statistics but will be considered in determining worst case values.

7.5.2. Analysis Methods

Actual values and changes from baseline will be summarized by treatment group at each scheduled timepoint.

A tabulation of the abnormalities per timepoint will be presented. This table will also show the number and percentage of subjects per abnormality, the number and percentage of subjects per treatment-emergent abnormality, and the cumulative number of subjects per treatment-emergent abnormality per post-baseline timepoint. Include in this table the safety follow-up visit, the Day 28 final study visit and the last study visit.

A cross-tabulation of the worst abnormalities versus baseline will be presented per phase (treatment and follow-up, treatment and follow-up phase and subperiods). This table will also show the number and percentage of subjects per worst abnormality, the number and percentage of subjects per treatment-emergent abnormality, and the cumulative number of subjects per treatment-emergent abnormality.

Mean \pm SE graphs over time for the actual values and changes from baseline will be generated for all tests performed.

A frequency tabulation of the QT/QTc change categories at Day 28 versus baseline will be presented.

ECG data for subjects having at least one treatment-emergent abnormality will be listed.

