- t. PRO assessments will be completed by all subjects at sites where appropriate PROs and translations are available and approved.

3. TIME AND EVENTS SCHEDULE – DURING HOSPITALIZATION (UP TO DISCHARGE), FOR PATIENTS WHO ENTERED THE OPTIONAL DOUBLE-BLIND EXTENSION TREATMENT ARM

Note: This Time and Events Schedule is only applicable for hospitalized patients who entered the treatment extension phase (see Sections 4.3 and 9.1.4 for eligibility criteria), and should be followed up to discharge.

Phase Day	Optional Extended Blinded Treatment ^a					Follow-up ^a						
	6	7	8	9	10	11	12-13	14	15-18	19	20-32	33 Safety Follow-up Visit / Final Study Visit ^a
Administration												
Administration of study drug ^b	X	X	X	X	X							
Virology												
Nasal MT swab for central testing ^c	X	X	X	X	X			X		X		
Endotracheal aspirate (only if intubated) ^e	X	X	X	X	X			X		X		
Efficacy/Safety												
Vital signs/pulse oximetry ^d	3x daily until discharge or through Day 19 (whichever comes first) ^e											X
Level of consciousness by ACVPU	3x daily until discharge or through Day 19 (whichever comes first) ^e											X
Physical exam												X
Symptom-directed physical exam	1x daily until discharge or through Day 19 (whichever comes first)											
12-lead ECG ^f												X
Pregnancy test (female subjects of childbearing potential)			X									X
Influenza Symptom Diary ^{l,m}	2x daily through the Final Study Visit/Safety Follow-up Visit											
Assessment of daily activities resumption ^{g,m}	1x daily through Final Study Visit/Safety Follow-up Visit											
PGIS ^{h,m}	1x daily through Final Study Visit/Safety Follow-up Visit											
PGIC ^{i,m}	X							X		X		X
EQ-5D ^{j,m}	X							X		X		X
Hematology, chemistry			X ^k			X ^k				X ^k		X ^k
Urinalysis			X			X				X		X
Adverse events recording	X	X	X	X	X	X	X	X	X	X	X	X
Prestudy and concomitant medication recording	X	X	X	X	X	X	X	X	X	X	X	X
Assessment of readiness for hospital discharge	1x daily until discharge or through Final Study Visit/Safety Follow-up Visit (whichever comes first)											
Assessment of ICU level of care requirement	1x daily until discharge or through Final Study Visit/Safety Follow-up Visit (whichever comes first)											

Abbreviations: ACVPU: alert, new confusion, voice, pain, unresponsive; ECG: electrocardiogram; EQ-5D: European Quality of Life 5 Dimensions; MT: mid-turbinate; PGIC: Patient Global Impression of Change; PGIS: Patient Global impression of Severity.

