- h. Questionnaire (PGIS) to be completed once daily onto the ePRO device.
- i. Questionnaire (PGIC) to be completed on Days 6, 14, 19, and 33 onto the ePRO device.
- j. Questionnaire (EQ-5D) to be completed on Days 6, 14, 19, and 33 onto the ePRO device.
- k. If feasible, safety blood samples will be collected after fasting for at least 10 hours.
- l. Influenza Symptom Dairy to be completed twice daily onto the ePRO device.
- m. PRO assessments will be completed by all subjects at sites where appropriate PROs and translations are available and approved.

4. TIME AND EVENTS SCHEDULE – AFTER DISCHARGE FROM HOSPITAL, FOR PATIENTS WHO HAD ENTERED THE OPTIONAL DOUBLE-BLIND EXTENSION TREATMENT ARM

Note: This Time and Events Schedule is only applicable for subjects who entered the treatment extension phase (see Sections 4.3 and 9.1.4 for eligibility criteria) and after they have been discharged. This Time and Events Schedule should start with the study day number following the day of discharge from the hospital (for example: subjects discharged on Study Day 6 would start with Day 7 procedures on this schedule). After subjects are discharged, the remainder of the study visits should be carried out as outpatient visits (preferably on-site or, if not feasible, at the subject's home) or by telephone follow-up as indicated in the table below. Every effort should be made to perform all of the assessments as outlined below (either on-site or at the subject's home), if practically feasible. In case of readmission to the hospital, subjects will continue to follow this Time and Events Schedule until the end of the study.

Phase	Optional Extended Blinded Treatment ^a	Follow-up ^a							
		Day	7-8-9-10	11 ^b	12-13	14 +/-1 Day	15-18	19 +/-1 Day	20-32
	Phone Follow-up ^c							Phone Follow-up ^d	Safety Follow-up Visit / Final Study Visit ^a
Clinic or home visit		X		X		X			X
Administration									
Administration of study drug ^{e,f}	X								
Virology									
Nasal MT swab for central testing ^g		X		X		X			
Efficacy/Safety									
Vital signs/pulse oximetry ^h		X							X
Physical exam									X
Symptom-directed physical exam		X		X		X			
12-lead ECG ⁱ									X
Pregnancy test (female subjects of childbearing potential)	X ^j								X
Influenza Symptom Diary ^{s,t}		2x daily through the Final Study Visit/Safety Follow-up Visit ^f							
Assessment of daily activities resumption ^{k,t}		1x daily through the Final Study Visit/Safety Follow-up Visit ^f							

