Subjects (1) who complete the 5-day treatment, (2) who are still hospitalized upon treatment completion, (3) who are on invasive mechanical ventilation or who have an ongoing respiratory deficiency as evidenced by having a peripheral capillary oxygen saturation (SpO₂) <94% on room air, or in case of known pre-influenza SpO₂ <94% (eg, due to COPD), the current blood oxygen saturation on room air is lower than pre-influenza infection levels by at least 3%, (4) who, in the opinion of the investigator, are expected to derive clinical benefit from extending the treatment period, and (5) for whom the investigator agrees to extend treatment with the same SOC will be given the option for treatment extension. In the second blinded course of treatment, subjects will continue treatment with pimodivir or placebo for another 5 days in combination with continued SOC treatment. If the SOC contained no influenza antiviral during the first treatment period, no influenza antiviral can be started in the treatment extension as part of the SOC

[figure not shown]
The study will consist of a screening/baseline visit, a double-blind treatment period of 5 days (with the possibility to extend the treatment period), and a follow-up period of 23 days after the last dosing day. The entire study duration for each subject will be 28 days, except for subjects receiving extended treatment, for whom the study will last 33 days. The study is considered complete with the completion of the last study assessment for the last subject participating in the study.

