2.1.4. Use of Records per Analysis Visit and Timepoint

To ensure only one record is used per analysis visit for the Return to daily activity and PGIS questionnaires only one questionnaire should be selected for analysis. Following rules should be followed to select the questionnaire.

1. The questionnaire latest in time is used.
2. If more than one questionnaire is still selected, the questionnaire with the highest sequence number is used.

To ensure only one record is used per analysis visit for the PGIC and EQ-5D questionnaires the following rules should be followed to select the questionnaire.

Listed below (Table 2) are the visit windows and the target days for each visit where PGIC and EQ-5D are recorded. The reference day is Study Day 1, the date of first intake of study drug.

1. If a subject has 2 or more actual visits in one visit window, the visit closest to the target day will be used as the protocol visit for that visit window.
2. If 2 actual visits are equidistant from the target day within a visit window, the later visit in time is used.

Table 2: Visit Windows for PGIC and EQ-5D

Scheduled Visit Number	Time Interval (label on output)	Time Interval (Day)*	Target Time Point (Day)
6	Day 6	[2 to 10]	6
14	Day 14	[11 to 20]	14
28	Day 28	[21 to 38]	28
For subjects on extended treatment:			
14	Day 14	[11 to 16]	14
19	Day 19	[17 to 22]	19
33	Day 33	[23 to 38]	33

*Relative to Study Day 1

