2.5. Baseline and Endpoint

The baseline analysis visit is defined as the last assessment before the first intake of the study drug, with the possible exception for height, weight, viral load results from the central lab testing and the hospital recovery scale (HRS). Height and weight are only recorded once, at screening/baseline visit, and the values recorded at this visit will be allocated to the baseline analysis visits irrespective of start of study drug. For viral load, if no measurement is available prior to first dose of study drug, then the first result from the central lab testing obtained up to and including 30 minutes after first dose of study drug will be considered as the baseline assessment and will be flagged in the analysis dataset. The baseline HRS is defined irrespective of the time of the start of study drug, and is covering the screening/baseline/day 1 visit which may be performed over two days as defined per protocol. Baseline HRS will be assigned to Day 1.

As specified in the protocol, an ECG recording within 1 calendar day before signing of the ICF/assent form can be used as baseline ECG requirement, if no ECG measurement was performed between signing ICF and first study drug intake.

For programming purposes the baseline record will be doubled in the ADAM datasets, the doubled record will be renamed with AVISIT = 'Baseline', AVISITN = 0 and will be assigned to the treatment phase.

For vital signs, NEWS2, ECG and central laboratory data the last study visit (Endpoint) is defined as the last scheduled study visit/timepoint and will be either the final study visit (day 28) or the safety follow-up visit.

For viral phenotyping, the last visit (Endpoint) is defined as the last study visit/timepoint for which an EC₅₀ and/or IC₅₀ result is available (including unscheduled visit results).

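### No SAP rule pools Day 33 with Day 28, so read literally the Day 28 EQ-5D and PGIC columns and one QT/QTc change table leave out subjects given the second course

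*SAP*

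**What the plan says.** **Protocol.** Section 3.1 sets two study lengths: "The entire study duration for each subject will be 28 days, except for subjects receiving extended treatment, for whom the study will last 33 days". Both follow from "a follow-up period of 23 days after the last dosing day". Section 4.3 offers the second course to subjects who have completed the first, are still in hospital, and are ventilated or still hypoxaemic, subject to the investigator's judgement.

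For subjects on the second course, Time and Events Schedule 3 (in hospital) has these footnotes: "Questionnaire (PGIC) to be completed on Days 6, 14, 19, and 33 onto the ePRO device" and "Questionnaire (EQ-5D) to be completed on Days 6, 14, 19, and 33 onto the ePRO device". Schedule 4 (after discharge) keeps Days 14, 19 and 33 for both instruments. The only ECG in either schedule is at the last visit, which Schedule 3 heads "33 Safety Follow-up Visit / Final Study Visit".

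**SAP.** Section 2.1.4 introduces Table 2: "Listed below (Table 2) are the visit windows and the target days for each visit where PGIC and EQ-5D are recorded". The upper block has Day 6 (window 2 to 10), Day 14 (11 to 20) and Day 28 (21 to 38). A second block, for subjects on extended treatment, has Day 14 (11 to 16), Day 19 (17 to 22) and Day 33 (23 to 38).

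Section 7.5.2 specifies, for the ECG: "A frequency tabulation of the QT/QTc change categories at Day 28 versus baseline will be presented". Section 2.5 says that the last study visit (Endpoint) for vital signs, NEWS2, ECG and laboratory data "will be either the final study visit (day 28) or the safety follow-up visit"; Day 33 is not named. Section 5.3.2.3 tabulates the EQ-5D VAS change categories (7 points or more, 10 points or more) without naming a visit and without a test.

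**The concern.** Extension is not a baseline characteristic. It is decided after the first course, mainly on whether the subject is still in hospital and still short of oxygen. A Day 28 EQ-5D or PGIC column without extended subjects is therefore a comparison of those who did not go on to a second course. If treatment affects who qualifies, the share removed will differ between arms, and the column no longer compares the groups as randomised.

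For the QT/QTc change categories, the one table devoted to them would lack the subjects who had two courses, including those on pimodivir who took up to 20 active doses.

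**Working it through.** **1. Reproduce the visit days.** One course: 5 + 23 = 28. Two courses: 10 + 23 = 33. Both match Protocol 3.1, so extended subjects have no scheduled Day 28 visit.

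**2. Compare what is collected with what is tabulated.**

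| Assessment | Non-extended | Extended | In a literal Day 28 display? |
|---|---|---|---|
| EQ-5D, PGIC | Days 6, 14, 28 | Days 6, 14, 19, 33 | Extended subjects absent |
| Scheduled post-baseline ECG | Day 28 | Day 33 | Absent from the QT/QTc change table |
| PGIS, daily activities | Daily to final visit | Daily to final visit | Present |

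(EQ-5D is also taken at baseline in both groups.)

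**3. Look for a pooling rule.** There is none. Under SAP 2.1.2, scheduled visits carry the label of their scheduled day. Table 2 gives the extended subjects' last questionnaire its own Day 33 label. SAP 2.5 names only Day 28 and the safety follow-up visit.

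**4. Check the planning inputs used for scale.** SAP 1.4 gives the placebo Day 6 distribution 30/30/25/5/5/5%, a common odds ratio of about 0.62 (38% reduction), 600 subjects and 90% power; alpha is 5% two-sided (SAP 5.1.1). Applying 0.62 to the odds of each worse-or-equal tail gives pimodivir 40.9/29.9/19.4/3.4/3.3/3.2%. The proportional-odds formula is N = 12(z₀.₉₇₅ + z₀.₉₀)² / [(ln OR)²(1 − Σp̄³)], where p̄ is the mean of the two arms in each category. It gives N = 601, against the stated 600, and 89.9% power at 600. The inputs reproduce the plan.

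**5. Rough ceiling on extension.** The documents give no extension rate. Categories 3 to 5 (in hospital needing oxygen, in ICU, or ventilated) are those in which the respiratory criterion could be met.

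- Placebo: 25 + 5 + 5 = 35.0%.
- Pimodivir: P(category ≥3) has odds (0.40/0.60) × 0.62 = 0.413, so 29.2%. P(death) has odds (0.05/0.95) × 0.62 = 0.0326, so 3.2%. The difference, from unrounded values, is 26.1%.

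With 300 per arm and an assumed uptake among these subjects:

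| Assumed uptake | Placebo omitted | Pimodivir omitted | Left of 600 |
|---|---|---|---|
| 25% | 26 | 20 | 554 |
| 50% | 53 | 39 | 508 |
| 100% | 105 | 78 | 417 |

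The arm difference in the omitted share is at most 35.0 − 26.1 = 8.9 percentage points. With no treatment effect, the expected share is the same in both arms.

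**The case against.** The strongest reply is that little is lost.

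- **Questionnaires.** EQ-5D and PGIC on Days 6 and 14 cover both groups, and Day 33 is reported under its own label. The VAS change categories are descriptive and lie outside the confirmatory hierarchy.
- **ECG.** SAP 7.5.2 also asks for changes from baseline at each scheduled timepoint, an abnormality table that adds the last study visit, and a worst-abnormality cross-tabulation. SAP Attachment 4 counts the QTc-change classes among the abnormalities, so a large Day 33 change can still appear.
- **Exposure.** Both final ECGs come 23 days after the last dosing day. Protocol 1.1 gives a terminal half-life of about 13 to 28 hours after single doses; 23 × 24 / 28 is about 20 half-lives at the longer value. Neither ECG is on drug, and the omitted subjects include the placebo extension arm.
- **Wording.** Table 2's upper block is not restricted to non-extended subjects and holds the only Day 6 row. If it applies to everyone, a Day 33 record falls in both 21 to 38 and 23 to 38. The protocol gives Day 28 and Day 33 the same visit title, so Day 28 may be shorthand for the final visit.

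The first three replies are correct and limit the point to specific displays. The fourth shows that the literal reading is not the only one, but it is also a reason to amend: two programmers could build different Day 28 columns from the same text.

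Two safeguards do not settle the matter. The treatment-extension subgroup in SAP Table 3 keeps the two groups apart instead of restoring the randomised comparison, and it is not listed for safety. The subperiod ECG tables do not isolate two-course subjects either: the treatment phase ends 24 hours after the last dose (SAP 2.1.1), so the Day 33 ECG falls in follow-up.

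**Conclusion.** The point holds for three displays, read literally: the Day 28 column for EQ-5D (including the late column of the VAS change categories), the Day 28 column for PGIC, and the QT/QTc change-category table. Each omits subjects given the second course, on a criterion observed after randomisation. This is a minor point, because these displays are descriptive and the data are collected.

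The size is unknown. The ceiling of 35.0% placebo against 26.1% pimodivir assumes the planning distribution, an odds ratio of 0.62, and that every subject in categories 3 to 5 extends. It is rough, because extension is judged on completing the course and also needs the investigator's agreement, not a Day 6 score.

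A reader might infer that all Day 28 summaries are affected, that the new EQ-5D endpoints as a whole compare a selected set, that QTc data on doubly exposed subjects are lost, or that a treatment difference is hidden. The documents do not support these readings. PGIS and daily activities are recorded daily, Days 6 and 14 include everyone, other ECG tables can carry Day 33, and only pimodivir-arm extended subjects had twice the drug exposure. Attenuation of an arm difference would require both a treatment effect on extension and worse late scores in extended subjects; it is possible, not shown.

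**What to change.** - **SAP 2.1.4, Table 2.** Keep the present windows: 21 to 38 with target Day 28 for non-extended subjects, and 23 to 38 with target Day 33 for extended subjects. State that the upper block's Day 14 and Day 28 rows apply to non-extended subjects only. Map both final windows to one analysis visit, *Final visit (Day 28/33)*, for the EQ-5D, PGIC and VAS change summaries. A single 21 to 38 window for everyone should be avoided: it would overlap the extended subjects' Day 19 window (17 to 22) on Days 21 and 22.
- **SAP 7.5.2.** Tabulate the QT/QTc change categories at the final visit (Day 28, or Day 33 if extended), overall and by number of courses.
- **SAP 2.5.** Define Endpoint as the final study visit (Day 28 or Day 33) or the safety follow-up visit.

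The cost is SAP wording and one mapping rule; no new data are needed. The downside is that extended subjects' questionnaires are read about 5 days later from study start, although both final visits are 23 days after the last dosing day.

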7.6. National Early Warning Score

7.6.1. Definitions

NEWS

The NEWS Score^[7] is an aggregated score with a range from 0 to 20 calculated as the sum of the scores per parameter (see Table 6, all parameters are based on the VS dataset and CM). However, in case information for a parameter is missing the NEWS score cannot be calculated.

Table 6: National Early Warning Score (NEWS)*

Physiological Parameters	3	2	1	0	1	2	3
Respiration Rate	≤8		9 - 11	12 - 20		21 - 24	≥25
Oxygen Saturations	≤91	92 - 93	94 - 95	≥96			
Any Supplemental Oxygen		Yes		No			
Temperature	≤35.0		35.1 - 36.0	36.1 - 38.0	38.1 - 39.0	≥39.1	
Systolic BP	≤90	91 - 100	101 - 110	111 - 219			≥220
Heart Rate	≤40		41 - 50	51 - 90	91 - 110	111 - 130	≥131
Level Of Consciousness				A			V,P, or U

*The NEWS initiative flowed from the Royal College of Physicians' NEWS Development and Implementation Group (NEWSDIG) report, and was jointly developed and funded in collaboration with the Royal College of Physicians, Royal College of Nursing, National Outreach Forum and NHS Training for Innovation

Note: The following parameters for the NEWS for subjects that are on invasive mechanically ventilation while NEWS is assessed will be adjusted:

Oxygen saturation = 90%

Any Supplemental oxygen = YES

Level of Consciousness = Unresponsive

The observed data values for these parameters will be ignored and replaced by above values. Subsequently all parameters will be evaluated according to Table 6.

NEWS2

The original NEWS was designed for patients whose normal range for oxygen saturation is between 96 – 100%. For SpO₂ values below this, the NEWS score increases. The NEWS is updated by a new version, NEWS2^[8], to more accurately score the acute-illness severity of subjects with routinely low oxygen saturation. Subjects that have a prescribed oxygen saturation requirement of

88 - 92%, i.e. patients with hypercapnic respiratory failure, often referred to as ‘type 2’ respiratory failure (Although COPD is the most common cause of hypercapnic respiratory failure, there are other causes such as morbid obesity, chest-wall deformities or neuromuscular disorders) will be evaluated with the new SpO₂ scoring scale 2.

In addition, a new consciousness level is added to capture a change in confusion: new Confusion (C). Note: The following parameters for the NEWS2 for subjects that are on invasive mechanical ventilation and that met the criteria for the SpO₂ scale 2 will be adjusted:

Oxygen saturation = 82%

Any Supplemental oxygen = YES

Level of Consciousness = Unresponsive

The observed data values for these parameters will be ignored and replaced by above values. Subsequently all parameters will be evaluated according to [Table 7](#)

Table 7: The NEWS2 scoring system

Physiological parameter	Score						
	3	2	1	0	1	2	3
Respiration rate (per minute)	≤8		9–11	12–20		21–24	≥25
SpO ₂ Scale 1 (%)	≤91	92–93	94–95	≥96			
SpO ₂ Scale 2 (%)	≤83	84–85	86–87	88–92 ≥93 on air	93–94 on oxygen	95–96 on oxygen	≥97 on oxygen
Air or oxygen?		Oxygen		Air			
Systolic blood pressure (mmHg)	≤90	91–100	101–110	111–219			≥220
Pulse (per minute)	≤40		41–50	51–90	91–110	111–130	≥131
Consciousness				Alert			CVPU
Temperature (°C)	≤35.0		35.1–36.0	36.1–38.0	38.1–39.0	≥39.1	

Note: the physiological parameter: ‘Air or Oxygen’ is evaluated by checking the use of the supplemental oxygen.

For the SpO₂ scale 2, to evaluate if the assessment is taken on room air or on oxygen, the answer to the question ‘Was this measurement taken on room air’ is used. Oxygen saturation measurements lower or equal to 92% are scored 0 to 3 in the SpO₂ scale 2 independent if the measurement was taken on room air or not. Oxygen saturation measurements of 92% or more on room air will have a score 0 for the SpO₂ scale 2. Oxygen saturation measurements of 93 or more taken on oxygen are scored 1 to 3 in the SpO₂ scale 2 (last 3 columns)

The subjects for who the oxygen saturations levels need to be evaluated with the SpO₂ scale 2, met following criteria at (or before) the time of randomization:

- Oxygen saturation of the last assessment before randomizing is lower or equal to 92%
- Chronic oxygen was used

The SpO₂ scale 2 will then be used for the NEWS2 calculation throughout the rest of the trial for the subject. The SpO₂ scale 1 will be used for the other subjects.

Note that for the NEWS2 by timepoint a subject receives supplemental oxygen if he received oxygen at the time of the measurement of oxygen saturation. For the NEWS(2) stratification this is checked within the randomization window as explained in Section 5.1.4

NEWS2 Category

The NEWS 2 will be categorized into its clinical risk according to the following categories:

- No clinical risk: (score 0)
- Low clinical risk: (score 1 – 4)
- Medium clinical risk: (score 5 – 6, or 1 individual parameter with a score 3)
- High clinical risk: (score 7 and more)

In case a parameter is missing to calculate the NEWS 2 but based on the available information the NEWS 2 is 7 or more, the NEWS2 category will be 'High clinical risk'.

